**3. To what extent do you feel that you have a healthy diet that meets your energy and nutritional needs?**

- a. To a small extent
- b. To some extent
- c. To a large extent
- d. Do not know

**4. How often do you participate in social activities?**

- a. Rarely
- b. Occasionally
- c. Often
- d. Do not know

**5. Think about how you have been feeling the past 7 days. To what extent did you feel...?**

*Note: Only choose one option for each line*

	Not at all	To a small extent	To some extent	To a large extent	Do not know
Happy					
Enthusiastic					
Calm and relaxed					
Worried					
Depressed or sad					
Irritated					
Lonely					
Concerned					

**6. Think about the past 7 days, to what extent did you...**

*Note: Only choose one option for each line*

	Not at all	To a small extent	To some extent	To a large extent	Do not know
Have trouble sleeping at night?					
Have trouble with oversleeping?					
Feel weak, with low energy?					
Experience a loss of appetite?					
Eat too much?					
Feel faint or dizzy?					

**7. All in all, how would you rate your health?**

- Very good
- Good
- Neither good nor poor
- Poor
- Very poor
- Do not know

**8. All in all, how happy are you with your life?**

- a. Not happy at all
- b. Dissatisfied
- c. Neither dissatisfied nor satisfied
- d. Satisfied
- e. Do not know

Under each heading, please tick the ONE box that best describes your health TODAY.

**MOBILITY**

I have no problems in walking about	
I have slight problems in walking about	
I have moderate problems in walking about	
I have severe problems in walking about	
I am unable to walk about	

**SELF-CARE**

I have no problems washing or dressing myself	
I have slight problems washing or dressing myself	
I have moderate problems washing or dressing myself	
I have severe problems washing or dressing myself	
I am unable to wash or dress myself	

**USUAL ACTIVITIES (e.g. work, study, housework, family or leisure activities)**

I have no problems doing my usual activities	
I have slight problems doing my usual activities	
I have moderate problems doing my usual activities	
I have severe problems doing my usual activities	
I am unable to do my usual activities	

**PAIN / DISCOMFORT**

[figure not shown]
I have no pain or discomfort	
I have slight pain or discomfort	
I have moderate pain or discomfort	
I have severe pain or discomfort	
I have extreme pain or discomfort	

**ANXIETY / DEPRESSION**

I am not anxious or depressed	
I am slightly anxious or depressed	
I am moderately anxious or depressed	
I am severely anxious or depressed	
I am extremely anxious or depressed	

- We would like to know how good or bad your health is TODAY.
- This scale is numbered from 0 to 100.
- 100 means the best health you can imagine.  
0 means the worst health you can imagine.
- Mark an X on the scale to indicate how your health is TODAY.
- Now, please write the number you marked on the scale in the box below.

YOUR HEALTH TODAY =

## Monitoring of own health

### 9. How do you perceive the following?

*Note: Only choose one option for each line*

	Not at all	To a small extent	To some extent	To a large extent	Do not know
To what extent do you feel in control of your own health?					
To what extent do you feel that your current state of health makes it difficult to plan your everyday life?					
To what extent do you feel that you understand your body's signals and symptoms?					
To what extent do you feel that your current state of health makes it difficult to realize your goals and abilities?					
To what extent do you feel satisfied with the follow-up of your health?					
To what extent do you feel that your regular general practitioner (GP) is adequately involved in following up your health?					
To what extent do you feel that you have the					

opportunity to contribute to your own treatment?					
--	--	--	--	--	--

**10. On average, during the past month, how did you register measurements and/or answer the questionnaire on your tablet?**

- a. More than once a day
- b. Once a day
- c. 4-6 times per week
- d. 2-3 times per week
- e. Once a week
- f. Less than once a week

**11. What type of technology do you use in connection with the follow-up on your tablet? *Choose more than one option if necessary***

- a. Tablet
- b. Scale
- c. Blood glucose monitor
- d. Blood pressure monitor
- e. Pulse Oximeter
- f. Spirometer
- g. Thermometer
- h. Capnograph
- i. Other

**12. Consider the following statements.**

*Note: Only choose one option for each line*

	Disagree	Neither agree nor disagree	Agree	Do not know
Registrations via the tablet are difficult to carry out				
Registrations via the tablet gives me too much responsibility for my own health				

The registrations via the tablet make me feel safer in everyday life				
Follow-up via the tablet does not fit my health condition				
Follow-up via the tablet does not affect my health				
Overall, the follow-up via the tablet is of good quality				

13. To what extent are the following aspects of the follow-up of your health via the tablet (telehealth monitoring) important to you?

*Note: Only choose one option for each line*

	Not at all	To a small extent	To some extent	To a large extent	Do not know/ not relevant
That health care professionals monitor my measurements/ answers my questions					
Being able to monitor my own measurements					
That I can contact the follow-up service if needed					

That the follow-up  
service sends me tips  
and advice related to  
my *health*

--	--	--	--	--	--

## **Background information**

**14. What is your gender?**

- a. Male**
- b. Female**
- c. Do not want to answer**

**15. What is your mother tongue?**

- a. Norwegian**
- b. Swedish, Danish eller Finnish**
- c. Other**
- d. Do not want to answer**

**16. In what year were you born?**

---

**17. What is your highest level of completed education?**

- a. Elementary school**
- b. Primary and lower secondary school**
- c. Upper secondary education**
- d. Higher education**
- e. Do not want to answer**

**18. What is your marital status?**

- a. Unmarried**
- b. Married/ cohabitant/ registered partner**
- c. Widow/widower**
- d. Divorced**
- e. Separated**
- f. Do not want to answer**

**19. What is your current living situation?**

- a. Live alone**
- b. Live with children**
- c. Live with spouse/ cohabitant/ registered partner**
- d. Live with parents/siblings/other**
- e. Live in residential care home, nursing home, house-share etc.**
- f. Do not want to answer**

**20. Do you regularly get help or care from someone who does not receive a salary to help you?**

*(For instance help with personal hygiene, cooking, house cleaning, or to keep track of appointments.)*

- a. Spouse/ cohabitant/ registered partner**
- b. Parents**
- c. Children**
- d. Neighbour**
- e. Friends/ acquaintances**
- f. Other family**
- g. Other**
- h. No, no I do not get help → Go to question 22**
- i. Do not want to answer → Go to question 22**

**21. How often do you get help or care from someone who does not receive a salary to help you?**

- a. Never**
- b. Once a month**
- c. 2-3 times per month**
- d. 1 day per week**
- e. 2-3 days per week**
- f. 4-5 days per week**
- g. 6-7 days per week**
- h. Do not want to answer**

**22. Do you use any of the following technological aids?**

- a. Safety alarm**
- b. Medication Dispenser**
- c. I do not use any of the technological aids mentioned above**
- d. Do not want to answer**

**23. What is your main source of income?**

- a. Own income**
- b. Pension**
- c. Social insurance**
- d. Other**
- e. Do not want to answer**

**24. What is your household's annual income before tax (salary, pension, sickness benefit, social insurance etc.)?**

- a. 0-200 000 NOK**
- b. 200 000-400 000 NOK**
- c. 400 000-600 000 NOK**
- d. 600 000-800 000 NOK**
- e. 800 000-1 000 000 NOK**
- f. 1-1.2 million NOK**
- g. 1.2-1.5 million NOK**
- h. 1.5-2 million NOK**
- i. More than 2 million NOK**

**25. Is there anything else you would like to share about the measurements/registrations, the tablet, the follow-up and the use of the technology?**

*Open answer*

**Thank you for your participation!**

## Appendix C: GP questionnaire

### Telehealth trial: Questionnaire for GPs with patients who are participating in the trial

#### Definition of telehealth monitoring

Telehealth monitoring is a broad concept that lacks a clear definition. When we refer to "telehealth monitoring" in this survey, we refer to telehealth monitoring provided within the framework of the test conducted by the Directorate of Health and your municipality. Below is a brief description:

Telehealth monitoring means that the patient can be followed up remotely by the health and care service using technological solutions. Users of remote monitoring can answer simple questions about their health status via a tablet, and take measurements related to their health status (eg blood pressure, weight, O2 saturation). The results are transferred from the measuring devices to the tablet so that the patient can easily see them and monitor their own results over time. The results are also transmitted digitally to a follow-up service. The response service / follow-up service contacts the patient in case of signs of deterioration and measurements beyond what are normal values for the individual. They provide medical professional support and guidance based on the patient's needs and plan for follow-up, and will, in consultation with the patient, consider whether they should contact their GP / emergency room.

Telehealth monitoring can provide better health and better patient experience through targeted use of health care resources. The distance follow-up initiative can come from a general practitioner, a hospital, the patient himself or another health professional. It is the GP who, in consultation with the patient, assesses whether distance follow-up may be appropriate and professionally justified for the individual. The GP will, together with the patient, nurse and any other relevant health personnel, prepare a plan for follow-up based on the patient's goals, symptom picture and risk of deterioration. This plan forms the basis for the follow-up content, frequency and contact point for the individual.

By "follow-up service", we mean the unit that monitors the registrations the users send via their tablets. The follow-up service has different names in different municipalities, including the follow-up service, the telemedicine center and the health guard

#### Inclusion and exclusion criteria:

The target group of the telehealth trial is patients with chronic diseases, with medium or high risk of worsening of one's condition, risk of re-hospitalization or increased need for health and care service. These patients have a high consumption of health care services and the target group consists largely of patients with non-communicable chronic diseases such as diabetes, colic, cardiovascular disease, mental disorders and cancer. This group often has several diagnoses, complex and large needs, and are in need of follow-up of their diseases.

Patients who are not competent to consent, patients who cannot use the tablet or the measuring devices, and patients with substance use disorders, shall not be included in the trial.

In this part of the questionnaire we ask how you experience these inclusion and exclusion criteria.

1. To what extent are you familiar with the inclusion and exclusion criteria for participation in the telehealth trial (other than they are described above)?  
 Not at all  
 To a small extent  
 To some extent  
 To a large extent  
 Do not know
2. To what extent do you feel that the inclusion criteria for participation in the trial are suitable?  
 Not at all  
 To a small extent  
 To some extent  
 To a large extent  
 Do not know
3. You have stated that you do not at all or to a small extent feel that the inclusion criteria for participation in the telehealth trial are suitable. Can you elaborate?
4. What proportion of patients on your patient list do you estimate meet the inclusion criteria for telehealth?  
 No one  
 1-4%  
 5-9%  
 10-14%  
 15-19%  
 More than 20%
5. How many patients have you considered for telehealth (by recruiting them yourself or receiving a request from the project administration)?
6. How many of these did you consider not suited for participation?
7. What was the reason you considered these people not suited for participation? (More than one answer is possible)  
 The patient's health  
 The patient's ability to use technology  
 Lack of time for follow-up of patient using telehealth  
 Lack of time to consider and understand what telehealth is  
 Other
8. You have stated that there was another reason why you considered one or more people not suited. Can you elaborate?
9. Do you have any other comments related to the inclusion and exclusion criteria for telehealth monitoring?

#### **The GP's assessment of the patient's suitability for participation in the trial of telehealth monitoring**

In the examination of telehealth monitoring, the Directorate of Health has decided that the general practitioner, who is responsible for the patients on his list, must assess whether each patient proposed is suitable to participate in the trial. In this section we ask about your opinions on this.

10. Do you think it is right that you as a GP should be involved in the assessment of the patient's suitability for telehealth monitoring?

- Yes
- No

11. You stated that you do not think it is appropriate that you as a GP should evaluate the patient's suitability for telehealth monitoring. Can you elaborate?

#### **Recruitment to medical distance monitoring**

In this section we ask questions related to the recruitment to telehealth monitoring.

12. To what extent do you feel your patients are interested in receiving telehealth monitoring (disregarding that the trial is conducted as a randomized controlled trial)?

- Not at all
- To a small extent
- To some extent
- To a large extent
- Do not know

13. Have you identified and recruited patients on your list?

- Yes
- No

14. How many patients have you recruited?

15. Have you systematically reviewed your patient list to identify patients who may be eligible for telehealth monitoring?

16. In what way did you go through your patient list (eg using Medrave)?

17. To what extent has the recruitment of patients for telehealth monitoring been time-consuming?

- Not at all
- To a small extent
- To some extent
- To a large extent
- Do not know

18. Do you have any other comments related to the recruitment of patients for the trial of telehealth monitoring?

19. How many patients on your list are currently participating in the telehealth monitoring trial (and are included in the intervention group)?

20. How much time do you spend in an average month on telehealth monitoring (both recruitment and follow-up of patients receiving distance monitoring)?

- Less than half an hour
- Between half an hour and one hour
- Between one and two hours
- Between three and five hours
- More than five hours

21. Do you experience any change in the total amount of time you spend (the number of consultations and the time per consultation) on an average patient using telehealth monitoring?

- Time spent is significantly reduced
- Time spent is somewhat reduced
- No noticeable change in time spent
- Time spent is somewhat increased

- Time spent is significantly increased

22. Do you have access to your patients' measurements?

- Yes, I have direct access via journal system or similar
- Yes, but only if the patient brings their tablet
- No

23. To what extent is it useful for you to have access to your patients' measurements?

- Not at all
- To a small extent
- To some extent
- To a large extent
- Do not know

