### 8.2.2 Data from surveys

As part of the evaluation, we will carry out three different surveys: to users, to general practitioners and to employees in the follow-up service. The surveys are used to obtain both quantitative and qualitative data. Quantitative data is obtained in areas where register data does not extend, e.g. in areas such as health status, quality of life, patient experience, as well as time spent and quantitative assessments of telehealth. The

questionnaires are also used to obtain information of a more qualitative nature, typically in the form of open questions about i.e., patient experience, or health personnel's assessments of recruitment, organization, benefits and challenges. The surveys are a useful supplement to interviews as they reach a larger number of respondents, thus providing more breadth than a limited range of interviews. Insights from the surveys can often be followed up in interviews and in this way the various data sources complement each other. An overview of the surveys is presented in Table 4.

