#### Your time spent:

In this part we ask about we ask you how you allocate your working time to different tasks. Think of an average work week.

6. How large is your overall job percentage related to telehealth follow-up?

- 0-20
- 21-40
- 41-60
- 61-80
- 81-100

7. Indicate (approximately) the percentage of your total working time spent on the following tasks related to telehealth monitoring? [indicate one number per line]

- Recruiting new patients (including information meetings, training/instruction, ancillary working and interdisciplinary work with the patients plan for follow-up)
- Phone calls with patients
- Assessment of measurements / results
- Communication with the GP (not interdisciplinary meetings in connection to starting the patient up with telehealth monitoring), other primary health care or specialist health care
- Other

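### The staff-time questions do not cleanly separate recruitment, start-up and follow-up, and the GP answer bands separately leave out 2–3 hours

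*Combined protocol and SAP*

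**What the plan says.** Section 8.2.2 names the surveys as the quantitative source where registers do not reach, and includes "as well as time spent and quantitative assessments of telehealth" in that remit. Table 4 fields the GP and follow-up service surveys twice, in Fall 2019 and Spring 2021.

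GP questionnaire (Appendix C):
- Question 20 asks "How much time do you spend in an average month on telehealth monitoring (both recruitment and follow-up of patients receiving distance monitoring". Its bands pass from "Between one and two hours" directly to "Between three and five hours", and the last is "More than five hours".
- Two nearby items touch the components without collecting hours. Question 17 asks "To what extent has the recruitment of patients for telehealth monitoring been time-consuming", on an ordinal scale. Question 21 asks "Do you experience any change in the total amount of time you spend (the number of consultations and the time per consultation", with answers from significantly reduced to significantly increased.

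Follow-up service questionnaire (Appendix D):
- Question 7 asks staff to divide their telehealth working time by percentage. The first line is "Recruiting new patients (including information meetings, training/instruction, ancillary working and interdisciplinary work with the patients plan for follow-up". Phone calls, assessment of measurements, communication with other providers, and other work have lines of their own.

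Section 5.3 places consent, the baseline questionnaire and randomisation inside the information meeting. Section 6.5 describes the cost-benefit analysis, including how costs fall on general practitioners and municipalities. It does not say how staff time becomes a cost, or how time spent on the trial itself is taken out.

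**The concern.** The cost-benefit analysis is meant to inform a decision on national implementation. A national service would not take research consent, hand out a research questionnaire, randomise patients or recruit controls. It would still identify suitable patients, have the GP assess them, train them and draw up a follow-up plan. To cost that service, the time data must allow trial-only work to be told apart from work that would continue.

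Question 20 merges everything a GP does. The first line of question 7 merges the trial-only meeting with start-up work. Once a wave has been fielded in this form, the split for that wave cannot be fully recovered. The missing band is a second, independent defect: it makes the coding of GP time less precise but has no part in the merging.

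**Working it through.** The documents give no staff-hour, labour-cost or recruitment-share figure, so there is no stated result to reproduce. The check has four parts.

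**1. Which items yield hours, and for what.** In Appendix C only question 20 does, as a single total. In Appendix D, question 7 isolates running-service work in its later lines, so the merging there is confined to the first line.

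**2. What the two waves can show.** Recruitment is due to end on 30.06.2020 (Table 8). Taking spring to begin in March, the second wave comes at least 8 months later.
- Fall 2019 contains start-up work, mixed with trial tasks.
- Spring 2021 should contain mainly ongoing follow-up if recruitment closes on plan, and so little start-up.
- Question 20 refers to an average month without saying which period, so a GP answering in 2021 may still average over the recruitment phase.

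Neither wave therefore isolates start-up time.

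**3. Sensitivity to the recruitment share.** Let r be the share of the question 20 total that is recruitment (unknown; values assumed). Follow-up time = total × (1 − r). An answer in the 3–5 hour band, coded at its midpoint of 4 h, gives:

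| r | follow-up time |
|---|---|
| 0% | 4 × 1.00 = 4 h |
| 25% | 4 × 0.75 = 3 h |
| 50% | 4 × 0.50 = 2 h |
| 75% | 4 × 0.25 = 1 h |

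This shows how little the total fixes; it does not estimate a bias. There is also an allocation effect. Question 19 counts only intervention patients, whereas recruitment effort is spent before the arm is known. If the total covers both arms, then under 1:1 allocation dividing question 20 by question 19 charges each user with the recruitment time of about two patients.

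**4. Band gap.** The band edges in hours are 0–0.5, 0.5–1, 1–2, 3–5 and above 5. The only break is 3 − 2 = 1 h. The plan gives no coding rule; with midpoints assumed (1.5 h and 4 h), the error is midpoint ÷ true − 1:
- True 2.5 h: 1.5/2.5 − 1 = −40%, or 4/2.5 − 1 = +60%.
- Across true times of just over 2 h to just under 3 h: about −25% to −50% if the lower band is ticked, about +99% to +34% if the upper.
- With a 2–3 h band (midpoint 2.5 h): about +24% to −16%.

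If 10% of GPs are at 2.5 h (assumed), mean GP time shifts by between 0.10 × (1.5 − 2.5) = −0.10 and 0.10 × (4 − 2.5) = +0.15 h a month. At 30% the limits are −0.30 and +0.45 h.

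**The case against.** A reader might infer that the cost-benefit analysis cannot separate service time from research time at all, that the error runs against telehealth, and that it is large. The documents do not support this.

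- **Partial separation exists.** Question 7 already sets recruitment apart from phone calls, measurement review and communication, and the Spring 2021 wave comes after planned recruitment closure. Appendix C also counts patients considered, judged unsuitable, recruited and currently in the intervention group (questions 5, 6, 14 and 19). Question 24 asks separately how often GPs contact the follow-up service about recruitment, planning and follow-up. An approximate breakdown is possible, and the 1:1 ratio is known. None of these items supplies hours, however, so the breakdown would rest on assumption.
- **Recruitment is not all research.** A project employee, not the GP, handles consent, questionnaire and randomisation (sections 5.3 and 5.4). The introduction to Appendix C presents the GP's suitability assessment as part of telehealth. Much GP recruitment time could recur in routine care, so a bias against telehealth is not established. Costing follow-up alone would err the other way and understate the service.
- **The surveys are one input among several.** Section 6.5 also draws on effect and process data, national statistics, interviews and literature, and section 8.2.4 seeks aggregated service data if obtainable. Table 4 lists time use as a theme only for the follow-up service survey. That question 20 feeds labour cost is a reasonable inference, not a stated plan. The primary cost endpoint (section 6.3) uses actual service use and public cost statistics and does not depend on it.
- **The gap may be a translation slip.** The appendix is in English while section 6 gives the question wording in Norwegian, and the printed appendices show other slips, such as colic where section 3.1 lists COPD.

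These points limit the claim. They leave standing that the only GP time item is a single total and that question 7 merges trial-only work with start-up work.

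**Conclusion.** The point holds in a limited form. As printed, the surveys do not let the cost-benefit analysis cleanly separate GP recruitment from GP follow-up, or research time from start-up time in the follow-up service. Ongoing service time is available only in part, and start-up time is not isolated in either wave.

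The size of any resulting bias in cost is unknown, because the recruitment share is not given; its direction is not established either. The band gap is a measurable but separate imprecision: −40% or +60% for a GP at 2.5 hours, assuming midpoint coding and that the fielded form has the same bands. Cost-effectiveness is an exploratory objective, so the trial's primary comparisons are unaffected. The change is still worth making, because it costs almost nothing before fielding and cannot be fully made good afterwards.

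**What to change.** Before the Fall 2019 mailing:

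1. **Appendix C, question 20.** Replace the single total with three items: (a) identifying, assessing and recruiting patients; (b) start-up and follow-up planning; (c) ongoing follow-up. Give each a stated reference period and contiguous bands, adding one for two to three hours. Check the fielded Norwegian form first to see whether the gap is there.
2. **Appendix D, question 7.** Split the first line into (a) information meeting, consent, questionnaire and randomisation, and (b) training and follow-up plan.
3. **Section 6.5.** State that the base-case service cost excludes only trial-only tasks: consent, the research questionnaire, randomisation, and recruitment time spent on control patients. Keep patient identification, GP suitability assessment, training and planning in the cost. Add a sensitivity analysis that includes all recruitment time. GPs need not report the control share; it can be derived from item (a) and the 1:1 allocation.

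The cost is a few extra lines in two electronic surveys and a short addition to section 6.5. The drawback is slightly longer questionnaires.
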